Care Team Implementation Survey: The perspectives of care team members will be elicited during implementation using the Care Team Implementation Survey. At baseline, the Care Team Implementation Survey consists of questions from two widely used implementation questionnaires: 1) the 12-item IAM-AIM-FIM survey, and 2) a 23-item instrument based on Normalization Process Theory (i.e., The NoMAD questionnaire). The NOMAD questions will assess, among other things, care team members' perceptions of intervention leadership, integrated workflow, training adequacy, and organizational understanding, as well as perceptions of the value of the intervention and its impact on working relationships. Just prior to initiation of the intervention (baseline), all care team members (e.g. physicians, nurses) within a given cluster will be invited to complete the surveys. Participants will be recruited at cluster engagement "kick-off" meetings and provided with a paper copy of the survey for completion. Care team members who are not recruited in-person will be sent an email link to complete the surveys online. Version 2 of the Care Team Implementation Survey will be repeated at 2-4 months after initiation of the intervention and 12 months later throughout the funding period, via email link or paper copy. Version 2 includes the same IAM-AIM-FIM and NoMAD questions, along with a set of questions that assess the care team members' current use of various components of E2C2. All surveys will be preceded with consenting information describing the study, risks, benefits, and alternatives, including the option to not participate.

Care Team Implementation Focus Groups: To supplement implementation survey data, members of care teams will also be invited by email to participate in focus groups. Up to two focus groups will be held with each cluster. A trained focus group facilitator will moderate the groups using a semi-structured interview guide informed by survey constructs (e.g., acceptability, integration of E2C2 into workflow), as well as the preliminary results of the cluster's survey data. Focus groups will function like reflective team meetings and will be recorded with permission and transcribed for analysis. Participants will complete oral consent prior to the focus group.

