Interviews will be conducted over the telephone or Zoom and are expected to last 30-45 minutes. If the patient prefers to use video conferencing, such as Zoom, the interview will be scheduled using a MC Health account, which is approved for PHI. They will be audio recorded with permission and transcribed for analysis and the video conference interview recorded. Upon completion of the interview, participants will be sent a hand-written thank you note. Participants will receive \$40 in remuneration for their time. The interview schedule will follow an iterative process of data collection and analysis, a standard technique in qualitative methodology designed to ensure the identification and testing of analytic categories until thematic saturation has been achieved. Methods of data analysis will be similar to those used for clinical stakeholders, although the study team will also include methods of framework analysis. Initial analysis steps are comparable to those for clinical stakeholder data, but the coding framework will be applied in order to generate a matrix of results,^{78,79} allowing for within- and across-case analysis. This approach will facilitate systematic but flexible analysis of variation in experiences by characteristics such as rural/urban and elderly/non-elderly.

See the below timeline for a summary of when clinical stakeholder and patient implementation data will be collected:

| | Pre E2C2, funding outset | Baseline** | 2-4 Months after Intervention Initiation | 6 Months after Intervention Initiation | 12 Months after last assessment |
|---|--------------------------|------------|--|--|---------------------------------|
| System-level practice stakeholder context assessment IAM-AIM-FIM surveys and interviews | X | | | | |
| Care Team Implementation Survey | | X | X | | X |
| Cluster implementation work focus groups * | | | X | | X |
| System implementation work key stakeholder interviews * | | | X | | X |
| System Stakeholder Sustainability Assessment | | | | | X |
| Interviews to assess patient disparities in implementation and outcomes* | | | | X | |

*Interviews and focus groups will commence following survey assessment.

**For survey administration, baseline refers to the period prior to implementation and just after the tool has been introduced to the care team.

Clusters

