Disease-focused clinical teams, e.g., breast, colorectal, etc. will comprise the clusters. All clusters will include both medical oncologists and mid-level providers.

Allocation. There will be 5 sequences in our design, with 3 clusters randomized to initiate the intervention for each sequence. Pre-E2C2 baseline assessment will occur for all clusters starting 7 months prior to the first sequence. Each sequence will occur 8 months apart; data collected prior to the intervention will provide a within-site control group for each site. The allocation is illustrated in **Figure 1**. To ensure balanced cluster characteristics we will stratify randomization based on cluster size and site.

Figure 1. Final allocation of 15 cancer care sites to 5 sequences over 6 time periods.

| Cluster | Strata | Step | | | | | | Sequence |
|--------------|--------|------|---|---|---|---|---|----------|
| | | 1 | 2 | 3 | 4 | 5 | 6 | |
| SWWI | 2 | 0 | 1 | 1 | 1 | 1 | 1 | |
| Rochester 1 | 1 | 0 | 1 | 1 | 1 | 1 | 1 | 011111 |
| Rochester 2 | 4 | 0 | 1 | 1 | 1 | 1 | 1 | |
| Rochester 3 | 2 | 0 | 0 | 1 | 1 | 1 | 1 | |
| Rochester 4 | 1 | 0 | 0 | 1 | 1 | 1 | 1 | 001111 |
| Rochester 5 | 4 | 0 | 0 | 1 | 1 | 1 | 1 | |
| Rochester 6 | 2 | 0 | 0 | 0 | 1 | 1 | 1 | |
| NWWI | 3 | 0 | 0 | 0 | 1 | 1 | 1 | 000111 |
| Rochester 7 | 1 | 0 | 0 | 0 | 1 | 1 | 1 | |
| SWMN | 3 | 0 | 0 | 0 | 0 | 1 | 1 | |
| Rochester 8 | 4 | 0 | 0 | 0 | 0 | 1 | 1 | 000011 |
| Rochester 9 | 1 | 0 | 0 | 0 | 0 | 1 | 1 | |
| Rochester 10 | 1 | 0 | 0 | 0 | 0 | 0 | 1 | |
| Rochester 11 | 1 | 0 | 0 | 0 | 0 | 0 | 1 | 000001 |
| SEMN | 2 | 0 | 0 | 0 | 0 | 0 | 1 | |

| | | | | | | |
|--|--|--|--|--|--|--|
| | | | | | | |
| | | | | | | |

Control condition

Intervention condition

T1 6 months

T2-T6 8 months

Interventions

The E2C2 intervention will include patient- and clinician-directed elements that are designed to increase the frequency with which patients receive individualized, preference-concordant, and guideline-based care for their symptoms and to increase rates of symptom control.

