Specific Aim 2 Analyses. We will summarize patient characteristics (sex, age, insurance status) by intervention status (baseline, intervention). We will also summarize all survey responses by cluster implementation status, including clinician characteristics (age, sex, years of practice). All patients will be analyzed on an intention to treat status; this principle will be extended to the cluster status, so that delays in implementation of an intervention will not affect the intervention status of patients.¹⁰¹ All methods will account for correlation of outcomes within clusters and across patients. As a secondary objective of this aim, we will assess the change in clinician survey constructs over time. This analysis will include each clinician with at least two completed surveys at least 6 months apart.

As in Aim 1, we will also assess the effect of process measures on SPPADE scores and other clinical outcomes. We will use models appropriate for count data, selecting standard or zero-inflated Poisson or negative binomial models according to Aikake's Information Criteria, or logit models for binary measures. For each outcome we will estimate a) bivariate models including only one survey score; b) a model with all scores; and c) a final model which also includes clinician characteristics.

Aim 3

Endpoints

Primary:

SPPADE and physical function NRSs will serve as both the E2C2 primary outcome and a critical component of the E2C2 intervention since NRS scores populate the EHR algorithms that determine whether patients are triaged to Level 1 or 2,

and whether patients are offered specific intervention components (education, medications, etc.). Patients will complete NRSs for SPPADE symptoms and physical function prior to medical oncology clinic appointments at all stages of the trial, i.e., prior to and after E2C2 initiation. ePROs will be more frequently administered to symptomatic patients outside of their appointment-linked assessments as part of the intervention. *To avoid potential bias from oversampling of symptomatic patients, only SPPADE symptom NRSs collected in association with clinic appointments will be included in the primary analysis.*

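### The 6-month rule in the clinician-survey change analysis excludes the baseline to 2-4 month pair, so entry in practice depends on answering a survey about 14-16 months after go-live

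*Combined protocol and SAP*

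**What the plan says.** All references are to the combined protocol and SAP.

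- **Data Analysis Plan, Specific Aim 2 Analyses.** The objective is "As a secondary objective of this aim, we will assess the change in clinician survey constructs over time". The inclusion rule follows directly: "This analysis will include each clinician with at least two completed surveys at least 6 months apart". No reason is given for the 6-month minimum.
- **Provider and staff data collection, Care Team Implementation Survey.** The first survey is given "Just prior to initiation of the intervention (baseline), all care team members" being invited. The second version, which repeats the same core instruments and adds questions on use of the system, "will be repeated at 2-4 months after initiation of the intervention and 12 months later throughout the funding period".
- **Timeline table for stakeholder and patient implementation data.** The columns match this schedule. The last is headed "12 Months after last assessment". A footnote says that, for surveys, "baseline refers to the period prior to implementation and just after the tool has been introduced to the care team".
- **Clusters, Allocation, and Figure 1.** "Each sequence will occur 8 months apart". The legend gives steps 2 to 6 a length of 8 months each. Sequence 5 consists of Rochester 10, Rochester 11 and SEMN.
- **Provider and staff data analysis, Care Team Implementation Surveys.** Scores by team or cluster and by tranche are planned at every scheduled wave, with differences explored between groups and over time. No 6-month rule applies there.

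**The concern.** The inclusion rule and the survey calendar do not fit each other well. Two of the three scheduled surveys sit on either side of go-live, and the gap between them is shorter than the rule requires. A clinician who completes both has repeat data on the same constructs, yet does not enter the only planned analysis that follows change within clinicians.

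Two things are at stake. First, repeat data that the trial collects anyway are set aside, which costs precision. Second, entry depends on still being in post and still responding more than a year after go-live. If late response is related to how clinicians view the system, the estimated change describes a selected group. Aim 2 concerns adoption and use, so the early change is of interest in its own right.

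**Working it through.** The plan gives no sample size, power or expected response rate for this analysis, so there is no stated figure to reproduce. The check is calendar arithmetic followed by an illustration.

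**Step 1: intervals between surveys.** Let L be the lead of the baseline survey before go-live, in months. L is not stated. The Care Team Implementation Survey section places survey 2 at 2-4 months after go-live and survey 3 twelve months after survey 2, that is, at 14-16 months.

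| Pair | Interval (months) | At least 6 months? |
|---|---|---|
| Baseline to survey 2 | L + 2 to L + 4 | No, if L is below 2 |
| Survey 2 to survey 3 | 12 | Yes |
| Baseline to survey 3 | L + 14 to L + 16 | Yes |

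For the first pair, L = 0 gives 2-4 months and L = 1 gives 3-5 months. At L = 2 the interval is 4-6 months, so only the latest survey-2 responders qualify. At L = 4 it is 6-8 months and all qualify. With L below 2 months, every qualifying pair contains survey 3 or a later one.

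**Step 2: does survey 3 fall inside the stepped wedge?** Let T1 be the length of step 1. The Allocation text gives 7 months and the Figure 1 legend gives 6. For sequence s:

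- Go-live = T1 + 8(s - 1)
- End of step 6 = T1 + 5 × 8 = T1 + 40
- Time from go-live to end of step 6 = 48 - 8s

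T1 cancels, so the 6 versus 7 discrepancy does not matter here.

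| Sequence | Go-live to end of step 6 (months) | Survey 3 at 14-16 months, relative to end of step 6 |
|---|---|---|
| 1 | 40 | 24-26 before |
| 2 | 32 | 16-18 before |
| 3 | 24 | 8-10 before |
| 4 | 16 | 0-2 before |
| 5 | 8 | 6-8 after |

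In calendar terms, survey 3 for sequence 5 falls at month 52-54 against an end of 46 (T1 = 6), or at month 53-55 against 47 (T1 = 7). If the third survey were read as 12 months after go-live, it would still fall 12 - 8 = 4 months after step 6.

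**Step 3: illustration of how many clinicians are excluded.** Assume three waves, response probability p at each, independent across waves, and L below 2 months. The values of p are assumptions.

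- At least two surveys: 3p²(1 - p) + p³
- Meets the rule (survey 3 plus at least one of the others): p[1 - (1 - p)²]
- Excluded despite repeat data (surveys 1 and 2 only): p²(1 - p)

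| p | At least two | Meets the rule | Excluded | Excluded as share of those with repeat data |
|---|---|---|---|---|
| 0.5 | 0.500 | 0.375 | 0.125 | 25% |
| 0.6 | 0.648 | 0.504 | 0.144 | 22% |
| 0.7 | 0.784 | 0.637 | 0.147 | 19% |

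**Step 4: sensitivity of that illustration.** If the survey repeats yearly, sequence 1 could have five waves within its 40 months (baseline, then 2-4, 14-16, 26-28 and 38-40 months). The proportion meeting the rule is then 1 - (1 - p)⁵ - 5p(1 - p)⁴ - p²(1 - p)³, which is 78%, 89% and 96% for p = 0.5, 0.6 and 0.7. The excluded share of those with repeat data falls to 0.031/0.813 = 4%, 0.023/0.913 = 3% and 0.013/0.969 = 1%. If the same clinicians always answer and the rest never do, nobody is excluded. A lower response at the third wave than at the first two would push the share up.

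**The case against.** The strongest reply is that the rule may be deliberate. A 6-month minimum is a sensible way to target longer-term change, and the Specific Aim 2 text never says that this analysis addresses the change from baseline to 2-4 months. Early change is described elsewhere: the Provider and staff data analysis section plans scores at every wave without the rule, and the Aim 2 text summarises all survey responses by implementation status. This stands in large part. A reader might infer that the early change goes unanalysed altogether, and the documents do not support that. What remains is that those summaries are at cluster and tranche level with no stated model, so they do not replace a within-clinician estimate, and the plan does not explain the rule.

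Three other inferences also go further than the documents allow:

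- **That sequence 5 has no eligible clinician.** The survey schedule is tied to the funding period, not to the end of step 6, and the timeline table makes no exception for late sequences. The three clusters are lost only if surveying stops before 14-16 months after their go-live.
- **That the baseline to 2-4 month pair can never qualify.** The lead time is not stated. A lead of 2 months or more is hard to square with a survey given just before go-live, but it is not ruled out.
- **That the retained clinicians are the more favourable ones.** This is plausible, but nothing in the documents shows it.

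**Conclusion.** The concern holds as a minor one. On the written schedule, and with a baseline lead under 2 months, the rule makes a survey at about 14-16 months or later a condition of entry. It also drops clinicians with only the first two surveys from the within-clinician analysis. This follows from the plan's own dates.

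The amount lost is not known. The 19-25% figure is an illustration that rests on assumed response of 50-70%, independence across waves and exactly three waves. It shrinks to a few per cent for early sequences if the survey repeats yearly. The contribution of the 3 clusters in sequence 5, out of 15 in the trial, depends on an end date for survey collection that the documents do not give.

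The analysis is a secondary objective of Aim 2 with no power statement or decision rule attached. The primary analysis of patient symptom scores is untouched.

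**What to change.** Replace the inclusion sentence in Specific Aim 2 Analyses with wording such as:

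> All completed care-team surveys will be analysed in a mixed model with survey wave (baseline, 2-4 months after go-live, 12 months later) as a categorical fixed effect and random effects for clinician and cluster. The changes from baseline to 2-4 months and from baseline to the third wave will both be reported. An analysis restricted to clinicians with surveys at least 6 months apart will be reported as a sensitivity analysis.

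If surveys repeat yearly, add the later waves as further categories. State also when survey collection ends and whether sequence 5 will receive its third survey. If longer-term change is the intended target, say so and give the reason for 6 months.

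The cost is SAP wording only, with no new data. The downside is that the model assumes survey non-response is explained by observed scores. That is still an assumption, but a weaker one than the restriction to pairs needs. Clinicians with a single survey inform the wave means but add nothing on within-person change, so the gain comes mainly from those with the first two surveys.

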E2C2 / 18-007779

Enhanced, EHR-facilitated Cancer Symptom Control (E2C2)
Pragmatic Clinical Trial

NCT03892967

Document Date: 03/04/2025

IRB Minimal Risk Protocol Template

General Study Information

Principal Investigator: [name], MSCE

Study Title: Enhanced, EHR-facilitated Cancer Symptom Control (E2C2) trial

Protocol version number: March 4, 2025 Version 24

Research Question and Aims

Hypothesis: Collaborative care management for control of moderate or worse sleep disturbance, pain, physical function impairment, anxiety, depression, fatigue (SPPADE symptoms), and physical dysfunction among cancer survivors and patients with cancer will improve quality of life, symptom severity, and adherence to cancer treatment, and will also reduce need for acute care.

Aims:

Specific Aim 1. Conduct a cluster randomized pragmatic trial with a stepped wedge design to test the hypothesis that a symptom control-focused E2C2 intervention will significantly reduce SPPADE symptom and physical dysfunction scores; reduce unplanned hospitalizations, emergency department (ED) visits, and intensive care unit (ICU) admissions; improve adherence to cancer therapies; and improve self-reported quality of life.

H1a. SPPADE symptom scores will improve more, relative to prior scores, for patients who have been exposed to the intervention when compared with the improvement of patients that are not exposed.

H1b. Among patients who report moderate or worse symptoms, SPPADE symptom scores will improve more for patients who have been exposed to the intervention when compared with the improvement of patients that are not exposed.

Specific Aim 2. Evaluate the hypothesis that use of a multifaceted, evidence-based implementation strategy to support adoption and use of the E2C2 system will result in improvements in implementation and clinical outcomes.

Specific Aim 3. Conduct a mixed methods evaluation to detect, understand and reduce disparities in the adoption and implementation of the E2C2 intervention among elderly and rural-dwelling patients with cancer.

Background:

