Automated Symptom Monitoring: Following the transition from pre-E2C2 usual care to the E2C2 intervention, the ePROs used to assess SPPADE symptoms, physical function impairment, social participation, distress, and QoL will not change, however, assessment frequency will increase, particularly for symptomatic patients. After initiating E2C2, the Symptom Control Bundle will be activated and patients and clinicians will be able to access graphic displays for SPPADE score tracking, and patients will be able to enter ePROM data via a telephonic symptom assessment in addition to the web, smart phone, and tablet modes.

Presentation of symptom data to patients and clinicians. For PROM data to be useful in clinical practice, patients and clinicians need to understand what the scores mean. In order to facilitate intuitive ePROM interpretation, the E2C2 intervention will include a dedicated view in the clinician-facing Synopsis section of the Epic EHR and in the patient-facing My Chart interface. The views will be identical for both patients and clinicians to support communication and will be specified per the findings of Snyder et al. to optimize accurate interpretation.⁸⁰ Data collected regarding symptom intensity and context will also be presented to clinicians in brief auto-generated text that will populate their clinical notes with a patient's longitudinal SPPADE scores and a hyperlink to the graphic Synopsis view. Presenting data to clinicians in graphic form for decision support has been shown to have a small to moderate effect size in improving patient outcomes.^{81,82}

EHR Triage and Decision Support Algorithms. EHR algorithms are foundational to the E2C2 intervention. Algorithms populated by automatically abstracted PROM and clinical data from the EHR will determine which symptom-directed services are offered to patients at multiple points in the intervention. Algorithms will be built into Epic using specification capabilities integral to the foundation system and available in all Epic iterations after 2014.

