We will summarize patient-, cluster-, and survey-level characteristics (e.g., sex, age, cancer type and stage, insurance status) by intervention status (pre-E2C2, E2C2) of the encounter. All analyses will be conducted on an intention to treat basis. The primary analysis will test differences in change in joint SPPADE symptom NRS scores in all participants, and in those who report elevated (4-10/10) symptoms, between participants who are exposed to the intervention and those who are not. We have two primary hypotheses. The first will assess the effect of the intervention across the full cohort of patients enrolled, Hypothesis *H1a*. The second will assess the effect of the intervention among patients who report moderate or worse symptoms, Hypothesis *H1b*. The rationale for Hypothesis *H1b* is that some intervention components are only offered to participants who report elevated symptom scores. Additionally, a large proportion of the trial cohort will only report mild or no symptoms. Among these participants there is little or no opportunity to improve symptoms and no practical exposure to the intervention. The original hypotheses regarding population-level effects will retain primary importance, yet it is critical to test intervention effects in the subset of patients that ever have elevated symptom scores.

We will include a common set of variables in all models testing the effectiveness of the intervention. Cancer type and stage will be included, as well as 7 variables selected as likely to impact the use of the portal and completion of the

[figure not shown]

Figure 3. Power simulations for E2C2 Interventions

surveys: from the EHR we will capture age (categorized into 10-year increments), sex (male or female), and severity of illness (Elixhauser score as a categorical variable). We will also link the patient 9-digit zip code to Census data to get estimates of educational level, income, and broadband access, which will be categorized into quartiles.

Hypotheses H1a

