Health care utilization. Healthcare utilization for E2C2 will consider health care encounters including hospitalizations, ED visits, ICU admissions, clinic outpatient visits, and calls to the oncology care team. EHR entries and administrative billing data will be aggregated to construct a comprehensive data set of all clinical encounters. Data collected for hospitalizations will include admission and discharge diagnoses, length of stay, ICU admission/transfer, and whether an admission was planned for anti-cancer treatment or unplanned, and if the latter, initiated from the ED or an office visit. For ED encounters, we will capture diagnoses and whether an encounter resulted in hospital or ICU admission. Clinic visits will be captured using billing data which will include CPT codes, ICD-10 codes, location, and clinician NPI numbers. We will be able to ascertain clinician discipline and specialty from the NPI numbers. Calls to the oncology care team are not billed but are reliably captured in the EHR. A recent audit established that 87% of calls to medical oncology practitioners were recorded in the EHR, and that rates of capture did not vary systematically across disciplines. However, call characteristics, e.g., duration, were not reliably recorded. Therefore we will use count data in analyses to model call frequency.

We will estimate mixed effects Poisson regression models with utilization events during the trial period as dependent variables. Because utilization events will be available for all trial participants, we will perform analyses with cohorts comprised of all trial participants and those who completed ≥ 1 ePROM, and ≥ 2 ePROMs.

The majority, but not all, of patients' health care utilization will occur at MC facilities. Established patterns suggest that 75% to 80% of patients care will occur at an MC facility and that this frequency will not vary across E2C2 clusters, or phases of the E2C2 intervention, e.g., pre-E2C2, Stage 1. However, we will perform analyses that include only patients residing within driving distance of a trial site to assess the impact of distance. Additionally, we will use imputation methods and sensitivity analyses to assess the impact of mis-ascertainment of utilization data.

Cancer treatment adherence. The literature does not offer a definitive definition of cancer treatment adherence, even

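### Each utilization outcome is analysed in three cohorts with none named as deciding, and entry to the cohort with at least two ePROMs depends on the intervention

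*Combined protocol and SAP*

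**What the plan says.** All references are to the combined protocol and SAP.

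- **Specific Aim 1** hypothesises that E2C2 will "reduce unplanned hospitalizations, emergency department (ED) visits, and intensive care unit (ICU) admissions".
- **Endpoints, Secondary, Health care utilization** covers "health care encounters including hospitalizations, ED visits, ICU admissions, clinic outpatient visits, and calls to the oncology care team". The method is given as "We will estimate mixed effects Poisson regression models with utilization events during the trial period as dependent variables". The next sentence sets the cohorts: "Because utilization events will be available for all trial participants", "we will perform analyses with cohorts comprised of all trial participants and those who completed" at least one and at least two ePROMs. It gives no ranking, no rule for discordant results, and no definition of which ePROMs count or over what period. The sensitivity analyses listed there concern distance from a site and mis-ascertained utilization, not selection on completion.
- **Data Analysis Plan, Specific Aim 1 Analyses**: "All analyses will be conducted on an intention to treat basis".
- **Interventions, Automated Symptom Monitoring**: after the switch to E2C2, "assessment frequency will increase, particularly for symptomatic patients", and "patients will be able to enter ePROM data via a telephonic symptom assessment in addition to the web, smart phone, and tablet modes".
- **Endpoints, Primary** says that the more frequent ePROs for symptomatic patients, outside appointments, belong to the intervention. To avoid oversampling those patients, it restricts the primary analysis to appointment-linked NRS scores. The utilization section does not repeat the restriction.

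**The concern.** There are two linked problems.

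First, five encounter types in three cohorts give 5 × 3 = 15 results, and the three outcomes in the Aim 1 hypothesis give 3 × 3 = 9. If the cohorts disagree, the plan does not say which result stands.

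Second, completing two ePROMs happens after enrolment and is partly a product of E2C2. A symptomatic patient who completes a single ePROM around appointments stays outside the cohort under usual care, but can enter it after go-live by answering an extra one. If symptomatic patients also use more acute care, the post-go-live cohort is sicker even when E2C2 does nothing. The comparison could then suggest more admissions or ED visits, or hide a real fall. The plan guards against this oversampling in its primary analysis but not here.

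**Working it through.** The documents give no significance level, event rate, completion rate or power for utilization, so there is no figure to reproduce. Everything below is illustrative and every numerical input is an assumption.

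**1. Selection into the cohorts when E2C2 has no effect**

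Assumed inputs:
- log-normal frailty with mean 1 and log-scale SD 0.7, proportional to the event rate;
- the top 40% in frailty are symptomatic;
- appointment ePROMs sent are Poisson with mean 4, and each is answered with probability p (0.3 to 0.7), unrelated to frailty;
- after go-live, symptomatic patients receive e extra ePROMs (1 to 4), but only if they have already completed one. This condition follows the natural reading of Triage to Level 1 or 2, where symptomatic patients are identified from their own questionnaire responses.

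Formulas:
- c0 = P(at least 2 completed, no extras) = 1 − exp(−4p)(1 + 4p)
- c1 = P(at least 2 completed, symptomatic, after go-live) = c0 + 4p·exp(−4p)·[1 − (1 − p)^e]
- mean frailty of the top 40% = Φ(0.7 − 0.253)/0.40 = 0.672/0.40 = 1.681; of the rest = 0.328/0.60 = 0.546
- rate ratio = (0.4·c1·1.681 + 0.6·c0·0.546) / (0.4·c1 + 0.6·c0), since mean frailty in the usual-care cohort is 1.00

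Results for the cohort with at least two ePROMs:
- p = 0.3, e = 4: c0 = 1 − 0.301 × 2.2 = 0.337; c1 = 0.337 + 0.361 × 0.760 = 0.612; ratio = 0.522/0.447 = **1.17**.
- p = 0.7, e = 1: c0 = 1 − 0.0608 × 3.8 = 0.769; c1 = 0.769 + 0.170 × 0.7 = 0.888; ratio = 0.849/0.817 = **1.04**.

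Simulation with these inputs gives the same 1.04 to 1.17. Two other simulations with the same broad inputs gave 1.02 to 1.16 and 1.03 to 1.12, so about 1.02 to 1.17 is the range to quote.

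In the other cohorts:
- All participants: 1.00.
- At least one ePROM: 1.00, because extras go only to patients who already have one.
- At least two, counting only appointment-linked ePROMs: c1 = c0, so 1.00.

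**2. If E2C2 changes whether patients respond at all**

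A separate null simulation assumed four ePROMs per patient, with sicker patients responding less under usual care. With no change in response, all cohorts gave 1.00. When E2C2 raised response equally, the ratios were 1.03 (at least one) and 1.06 (at least two). When it drew in sicker patients more, they were 1.06 to 1.07 and 1.14 to 1.21. With lower baseline completion they were 1.13 and 1.33.

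Whether this route exists is unclear. Automated Symptom Monitoring lists telephone entry among the changes under E2C2, while Overall Study Design describes interactive voice response as part of the general questionnaire process.

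**3. Choosing among three results**

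Assume a two-sided 0.05 level, equal correlation between the three test statistics, and a claim made if any one is significant. The chance of at least one false positive per outcome is 12.5%, 9.8% and 8.4% at correlations 0.5, 0.8 and 0.9, so about 8% to 13%. The documents give neither the level nor the correlations, and they contain no rule that one cohort is enough.

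**The case against.** The best reply is that the plan already leans the right way. The Specific Aim 1 analyses section adopts intention to treat and keeps the population-level hypotheses foremost. The utilization section lists all participants first and explains that the data exist for everyone. The narrower cohorts also have a visible purpose: the H1a model needs a baseline and a later score, which matches at least two ePROMs, and its replication with single-survey patients matches at least one. They look like alignment cohorts rather than rival answers. This stands. A reader might infer that the plan contradicts its own intention-to-treat rule, but adding narrower cohorts beside an all-participant analysis does not. What is missing is the ranking.

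A reader might also infer that both completer cohorts are biased by the extra ePROs. The documents do not support that for the cohort with at least one, since extras appear to follow a completed questionnaire. Clinician referral is another way into Level 2, but nothing says that it triggers extra questionnaires.

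Finally, the ratios above are unadjusted and treat the two conditions as separate sets of patients. The planned models are mixed effects Poisson, the common covariate set includes cancer type, stage and Elixhauser score, and patients can contribute before and after go-live. These features may reduce the distortion. The range shows that bias can arise, not how large it will be in the planned analysis.

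**Conclusion.** The point holds in limited form. No cohort is named as deciding for any utilization outcome, and entry to the cohort with at least two ePROMs depends on the intervention because the section does not say which ePROMs count. With no true effect, the illustrative rate ratio there is about 1.02 to 1.17, against 1.00 in all participants. The size and direction rest on assumed frailty, response and extra-ePRO inputs, without covariate adjustment. On these inputs the distortion runs against E2C2.

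For the cohort with at least one ePROM, bias requires a change in whether patients respond, which the documents leave open. The 8% to 13% figure describes selective claiming under assumed inputs; it is not an error rate of the plan as written. These are secondary outcomes, and the primary SPPADE analysis is not affected.

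**What to change.** In Endpoints, Secondary, Health care utilization:

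1. Name the all-participants cohort as deciding for each utilization outcome.
2. Label the cohorts with at least one and at least two ePROMs as sensitivity analyses, aligned with the SPPADE analysis populations, that cannot support a claim alone.
3. Count only appointment-linked ePROMs toward entry to those cohorts, as the primary endpoint section does for NRS scores, and state the period over which they are counted.

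Separately, reconcile Overall Study Design with Automated Symptom Monitoring on whether telephone entry exists before E2C2.

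The cost is wording only: the all-participants analysis is already planned and needs no new data. The downside is that no claim can rest on the completer cohorts. Restricting to appointment-linked ePROMs closes the extra-ePRO route but not a change in response itself, which is a further reason to keep those cohorts supportive.
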